6.1.1. Vitals, ECGs and Cardiac Echocardiogram

Baseline values for vital signs, ECG and Cardiac Echocardiogram will be the last acceptable pre-dose measurement taken either on the day of dosing or at the baseline or screening visit.

If not supplied, QTcF will be derived using Fridericia's heart rate correction formula: QTcF = $QT / (RR)^{(1/3)}$, where RR = 60/HR (if RR is not provided).

Echocardiograms should be collected at times specified in the Schedule of Activities (please see protocol). To ensure safety of the subjects, a qualified individual at the investigator site will evaluate the echocardiogram for ejection fraction (EF) and left ventricular end systolic volume (LVESV).

6.1.2. Laboratory Data

Using the current Pfizer data standards, the last pre-dose value before the first day of dosing is used as the baseline for all laboratory parameters.

Clinical laboratory tests include hematology with complete blood count and differential, comprehensive metabolic panel (sodium, potassium, chloride, carbon dioxide, blood urea nitrogen, creatinine, calcium, glucose, total protein, albumin, total bilirubin, AST, ALT, alkaline phosphatase), cardiac troponin I, gamma-glutamyl transferase (GGT), prothrombin time (PT), activated partial thromboplastin time (aPTT), creatine kinase, amylase and urinalysis. If total bilirubin is abnormal, direct bilirubin will be tested reflexively. The samples for serum ferritin, serum iron, transferrin saturation and TIBC should be collected in the morning following an 8 hour fast. Hormone testing will include LH,FSH and estrogen in female subjects only. Laboratory monitoring will also be performed to detect ADA and NAb.

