# **SCHEDULE OF ACTIVITIES**

## Table 1 Cohort 1

	Screen	Lead- In		w-up	Early With- drawal								
				_		A (:	5 mg/kg	g)			19 (449 ±3)	20 (561 ±3)	
Visit Number (Study Day Visit	1 (-125	2 (-111	3 (1)	4 (29 ±3)	5 (57 ±3)	6 (85 ±3)	7 (113 ±3)	8 (141 ±3)	9 (169 ±3)	10 (197 ±3)			
Window) a	to -112)	to - 110)				B (4	0 mg/kg	g)					
		110)	11 (225 ±3)	12 (25 3 ±3)	13 (28 1 ± 3)	14 (30 9 ±3)	15 (337 ±3)	16 (365 ±3)	17 (393 ±3)	18 (421 ±3)			
Entry/Safety Assessme	ents	 		±3)	- 3)	 )							
Informed Consent	X												
Demography	Х												
Medical History b	X												
Medication History	X												
Inclusion/Exclusion	X												
Enrollment c	X												
Physical Examination	X	X	Х			X					X	X	Х
Pregnancy Test d	X	Х	X	Х	X	X	X	Х	X	Х	Х	Х	Х
Diary Cards d	X	X	X	Х	X	X	Х	Х	X	Х	X	X	Х
Contraception Review	X	X	X	Х	X	X	Х	Х	Х	Х	Х	Х	Х
Height		Х											
Weight e	Х	Х	X	Х	X	X	Х	X	X	Х	X	X	Х
Vital Signs f	Х	Х	Х	Х	X	X	Х	Х	Х	Х	Х	Х	Х

	Screen	Lead- In				Tr	eatmen	t			Follo	w-up	Early With- drawal
						A (:	5 mg/kg	g)			19 (449 ±3)	20 (561 ±3)	
Visit Number (Study Day Visit	1 (-125	2 (-111	3 (1)	4 (29 ±3)	5 (57 ±3)	6 (85 ±3)	7 (113 ±3)	8 (141 ±3)	9 (169 ±3)	10 (197 ±3)			
Window) a	to -112)	to - 110)				B (4	0 mg/kg	g)					
		110)	11 (225 ±3)	12 (25 3 ±3)	13 (28 1± 3)	14 (30 9 ±3)	15 (337 ±3)	16 (365 ±3)	17 (393 ±3)	18 (421 ±3)			
12- lead ECG	Х		Х		, í	X					X	Х	Х
Echocardiogram	Х										X	Х	Х
Clinical Laboratory Tests g	Х		X	Х	X	X	Х	Х	X	Х	Х	Х	Х
Serum Ferritin, Serum Iron, Transferrin Saturation, TIBC	Х		X	X	X	X	Х	X	X	Х	X	х	Х
Hormone Testing (LH, FSH, estrogen) h	Х	X	X	Х	X	X	Х	Х	X	Х	X	Х	Х
GLDH	X	X	X	Х	X	X	Х	X	X	Х	X	Х	Х
Fecal Occult Blood i	Х		Х	Х	X	X	Х	X	X	Х	X	Х	Х
C-SSRS	Х	X	X	Х	X	X	Х	X	X	Х	X	Х	Х
Imaging Assessments													
MRI-Liver	X		Xº			X					X	X	Х
MRI-Muscle j		Х	Х								Х	X	Х
DXA Whole Body		X	Х								X	X	Х
DXA Spine and Hip			X								X	X	X
Functional Assessmen	ts												
Muscle Strength		X	X				X				X	X	Х

	Screen	Lead- In	Treatment									w-up	Early With- drawal
						Δ (	5 mg/kg	ı)			19 (449 ±3)	20 (561 ±3)	
Visit Number (Study Day Visit	1 (-125	2 (-111	3 (1)	4 (29 ±3)	5 (57 ±3)	$     \begin{array}{c}       6 \\       (85 \\       \pm 3)     \end{array} $	$\frac{5 \text{ mg/ kg}}{7}$ (113 ±3)	8 (141 ±3)	9 (169 ±3)	10 (197 ±3)		)	

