### 6.1. Screening: Visit 1 (Screening Day -125 to -112)

During screening, subjects will be assessed for study eligibility. All screening must be completed and reviewed for subject eligibility before the subject is enrolled into the study. Screening laboratory tests with results considered by the investigator to be transient and inconsistent with the subject's clinical condition may be repeated once during the screening period for confirmation of eligibility. Imaging based examinations for screening must be reviewed before the subject is enrolled to assure an adequate baseline image has been acquired. If the image is determined to be of poor quality, it will be repeated. The visit window (Day -125 to -112) for screening is to allow for the analysis of laboratory testing, assurance of imaging quality and to provide multiple days to perform the assessments in the order described below. As soon as this is completed and subject's eligibility has been confirmed, they may be randomized into the study.

- **Informed Consent:** The subject must sign the informed consent document (ICD) prior to initiation of any screening assessments.
- Demographics: Information such as date of birth, race, and gender will be collected.
- Medical History: Medical history will include confirmation by genetic testing of the diagnosis of LGMD2I as obtained as reported from an appropriate regulated laboratory using a clinically validated genetic test (genetic testing is not provided by the sponsor). Results must confirm the biallelic alteration in the FKRP gene known to be or likely to be pathogenic and associated with LGMD2I. The mutation type will be reported. Medical history will also be reviewed for any significant medical/surgical histories and concurrent illnesses that required or are requiring specialist consultation or treatment.

- **Medication History:** Complete history will include all prescription or nonprescription drugs, and dietary and herbal supplements taken within 28 days prior to the planned first dose.
- Physical Examination, including Nose and Throat Mucosal Exam
- **Pregnancy Test**: A highly sensitive urine pregnancy test will be performed on all women of childbearing potential (WOCBP).
- **Diary Cards:** Will be provided with instructions to all WOCBP to record the first day of each menstruation cycle.
- Contraception Review: Confirmation of use of acceptable forms of contraception.
- Weight

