## 6.2. Lead-in Period: Visit 2 (Baseline Day -111 to -110 prior to dosing on Day 1)

The following procedures and studies should be performed in the morning (before noon) of Visit 2 whenever possible

- Physical Examination, including Nose and Throat Mucosal Exam
- **Pregnancy Test**: A highly sensitive urine pregnancy test will be performed on all female subjects and must be confirmed as negative within 1 month of receiving first dose.
- Diary Cards: For collection of first day of each menstrual cycle for WOCBP.
- Contraception Review: Confirmation of use of acceptable forms of contraception
- Height: Height should be measured in the morning.
- Weight
- Vital signs: Supine blood pressure, pulse rate, respiratory rate, and oral temperature.
- Horomone Testing: LH, FSH, estrogen in WOCBP
- GLDH
- C-SSRS
- **MRI-muscle:** WB-MRI and dedicated thigh MRI will be performed for muscle quantity and quality

The following procedures should be performed in the afternoon of Visit 2 whenever possible:

- **DXA:** Whole body DXA will be performed for lean body mass.
- **Functional assessments:** Must be conducted in the following order: Respiratory function (FVC, FEV1, MIP, MEP), 4SC, 2MWT, 10-meter walk/run, TUG, strength assessment (MMT, hand-held dynamometry) and PUL.
- **Needle muscle biopsy:** Following WB-MRI and functional assessments a needle muscle biopsy of the tibialis muscle will be performed.
- PD sample collection

- **Biomarker collection:** Blood will be collected for proteomic, metabolomic, and genomic biomarker analysis
- Adverse event monitoring
- Concommitant medications

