6.2.3. PD Endpoints

The baseline for all pharmacodynamics endpoints is the last pre-dose value before the first day of dosing.

Graphical analysis of total GDF-8 levels as absolute and percentage of baseline will be performed. Analyses will be employed to determine the effects of dose and concentration on the GDF-8 levels over time. The GDF-8 concentrations will be summarized descriptively by treatment and time points.

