8.2.1. Safety Analysis

For all safety variables and vital signs, the baseline will be predose measurement taken either on the day of dosing or at the baseline or screening visit.

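### The SAP's laboratory and PD baseline conflicts with SAP 8.2.1 and can discard the Visit 3 pre-dose sample, so baseline age could vary from about 1 day to over 16 weeks

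*SAP*

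**What the plan says.** SAP 6.1.2 states that "the last pre-dose value before the first day of dosing is used as the baseline for all laboratory parameters". SAP 6.2.3 repeats the rule for PD: "The baseline for all pharmacodynamics endpoints is the last pre-dose value before the first day of dosing".

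Two other SAP sections admit a value from the dosing day itself. For vital signs, ECG and echocardiogram (SAP 6.1.1), the baseline "will be the last acceptable pre-dose measurement taken either on the day of dosing or at the baseline or screening visit". SAP 8.2.1, which covers every safety variable, says that "the baseline will be predose measurement taken either on the day of dosing or at the baseline or screening visit". Laboratory findings are a primary safety endpoint (SAP 4.2.1), so both 6.1.2 and 8.2.1 apply to them.

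On timing, the protocol labels Visit 3 as Day 1, and its section 6 identifies Day 1 as the first dosing day. Protocol 6.3 spreads Visit 3 over two days and places dosing after the second day's tests. Its heading for that second day still carries the Day 1 label.

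Schedule of Activities Tables 1 and 2 mark the clinical panel, iron indices and fecal occult blood at Visits 1 and 3 but not at Visit 2. GLDH and LH/FSH/estrogen are marked at all three visits, and immunogenicity first at Visit 3. For GDF-8 the tables differ: Table 1 (Cohort 1) has no Visit 2 mark and Table 2 (Cohorts 2 and 3) has one. Protocol 6.2 lists "PD sample collection" at Visit 2 without restriction by cohort.

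**The concern.** The sections differ on whether a pre-dose sample taken on the dosing day may be the baseline. SAP 6.1.1 and 8.2.1 say yes. SAP 6.1.2 and 6.2.3, read as written, say no. The schedule makes this matter, because several measures have no sample between screening and Visit 3.

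Two kinds of output depend on the answer. SAP Appendix 1 plans change and percent change from baseline in the serum iron indices (Table 14.1.1.30), which bear on the hepatic iron risk described in Protocol 1.12.1. SAP 6.2.3 and Table 14.1.1.115 plan GDF-8 as percentage of, and change from, baseline.

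A baseline from before the lead-in would mix untreated change with change on treatment. For some analytes it would also be a selected value. Protocol 4.1 and 4.2 set screening limits on GGT, alkaline phosphatase, bilirubin, serum iron and ferritin, among others, and allow one repeat of a result judged transient. Values admitted only below a ceiling tend to be higher when next measured, which is the direction of the signal being watched.

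**Working it through.** The plan gives no figure to reproduce. The check applies each baseline rule to the schedule.

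**Age of the fallback values.** For a sample on Day d (d negative), the gap to Day 1 is 1 − d if a Day 0 is counted and −d if not.

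- Visit 1, Day -125 to -112: 1 + 125 = 126 or 125 days at the early end; 1 + 112 = 113 or 112 days at the late end. Range 112 to 126 days (16.0 to 18.0 weeks).
- Visit 2, Day -111 to -110: 1 + 111 = 112 or 111 days; 1 + 110 = 111 or 110 days. Range 110 to 112 days (15.7 to 16.0 weeks).
- Footnote a to the schedule lets the Cohort 2 lead-in be extended, which lengthens each gap by the extension.

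**Which sample each rule selects.**

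| Measure | Pre-treatment samples | Visit 3 counts | Visit 3 excluded | Gap if excluded (days) |
|---|---|---|---|---|
| Clinical panel, iron indices | Visits 1, 3 | Visit 3 | Visit 1 | 112–126 |
| Fecal occult blood | Visits 1, 3 | Visit 3 | Visit 1 | 112–126, by visit day |
| GLDH, LH/FSH/estrogen | Visits 1, 2, 3 | Visit 3 | Visit 2 | 110–112 |
| ADA | Visit 3 | Visit 3 | none | – |
| GDF-8, Cohorts 2 and 3 | Visits 2, 3 | Visit 3 | Visit 2 | 110–112 |
| GDF-8, Cohort 1, by Schedule Table 1 | Visit 3 | Visit 3 | none | – |
| GDF-8, Cohort 1, by Protocol 6.2 | Visits 2, 3 | Visit 3 | Visit 2 | 110–112 |
| Muscle volume on MRI (PD in SAP 4.2.2.2) | Visits 2, 3 | Visit 3 | Visit 2 | 110–112 |

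Fecal samples are collected at home in the week before the visit. Their Visit 3 result is therefore lost only if exclusion goes by the Day 1 label, not by collection date.

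**When Visit 3 is excluded.** There are two routes: the sample is taken on the day of the infusion, or the program drops whatever carries the Day 1 label. If the blood is taken on the calendar day before the infusion and the program uses actual dates, the sample satisfies SAP 6.1.2 and 6.2.3 as written, with a gap of about 1 day. The day of the draw is therefore what decides. Footnote a puts the fasting draw on the first of the two days but calls that order preferred. For PK/PD the schedule asks only for a pre-dose sample.

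**Under one rule that includes Visit 3.** Every measure in the table has a Visit 3 baseline in all three cohorts. For the samples taken at the visit, the gap is 0 to 1 day.

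**The case against.** The strongest reply is that the planned order already avoids the problem. Protocol 6.3 lists the bloods in the block before the second day of Visit 3, gives the second day only functional tests and biopsy, and doses after that. Followed in that order, the bloods precede the dosing day and nothing falls back. This stands as a description of the preferred sequence, but it is no safeguard: the order is not required, and both days carry the Day 1 label.

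A reader might infer that all 20 subjects have a screening baseline for laboratory data. The documents do not support that. It ignores the preferred order and SAP 8.2.1, and it is wrong for GLDH and the hormones, which have a Visit 2 sample. The selection argument is also partial, since no screening limit is set for ALT, AST, transferrin saturation, TIBC, creatine kinase, troponin or GLDH.

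A reader might also infer that the 4 subjects in Cohort 1 have no GDF-8 baseline. That needs two adverse readings together: Visit 3 excluded, and Schedule Table 1 overriding Protocol 6.2.

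It is fair to add that the uses are descriptive. Protocol 9.3.5 plans no formal analysis of laboratory data, Table 14.1.1.29 disregards baseline abnormality, and the numerical escalation and stopping criteria are absolute R2* values. SAP 6.1.2 also invokes sponsor data standards that the reader cannot see. These points limit the harm. They do not settle which rule applies.

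**Conclusion.** The point holds as an unresolved conflict between baseline rules. The text of SAP 6.1.2 and 6.2.3 can discard the Visit 3 pre-dose sample, while SAP 8.2.1 would keep it for safety variables. Depending on the day of the draw and on how Day 1 is programmed, baseline age could differ between subjects from about 1 day to over 16 weeks, or longer with an extended Cohort 2 lead-in. In the worst case ADA has no baseline in any cohort.

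The number of subjects affected is not established, because it depends on draw dates that the documents do not fix. The bias from drift and selection cannot be sized either, since no within-subject variability is given.

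Two features suggest that Visit 3 was meant to count: Protocol 6.3 calls the Visit 3 immunogenicity sample the baseline, and SAP 8.2.2 measures functional change from Visit 3. If so, the SAP should say it. The consequence is confined to descriptive change-from-baseline outputs, chiefly the iron indices and GDF-8, but the iron indices are safety measures and the correction costs little.

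**What to change.** Use one sentence in SAP 6.1.2, 6.2.3 and 8.2.1: baseline is the last non-missing value before the start of the first infusion, including the Visit 3 pre-dose sample. State that this goes by actual collection date and time, not by visit label. SAP 8.2.1 needs the edit too, because as worded it neither asks for the last value nor says that the dosing day is the first one.

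Reconcile Schedule of Activities Table 1 with Table 2 and Protocol 6.2 on whether Cohort 1 has a PD sample at Visit 2.

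The cost is three SAP sentences and one schedule or text correction. No new Visit 3 sampling is needed, because those samples are already scheduled in all cohorts.

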6.1.3. Adverse Events

Severity is the key baseline information for adverse events. To judge an increase in adverse event severity after dosing, the post-dosing adverse event severity will be compared to the adverse event severity reported prior to the first day of study drug administration will be used.

6.1.4. Physical Examination/Nose and Throat Exam

The physical examination will include head, ears, eyes, nose, mouth, skin, heart and lung examinations, lymph nodes, gastrointestinal musculoskeletal, and neurological systems. A targeted and throat muscosal exam will be performed according to the Protocol's Schedule of Activities to monitor for any signs of mucosal telangiectasias.

6.2. Secondary Endpoints

- Mean change from baseline on function tests including PUL, Timed up-and-go (TUG), 10-meter walk/run (10MR), 2-meter walk test (2MWT), and 4 stair climb (4SC).
- Mean change from baseline on pulmonary function tests including forced vital capacity (FVC), FEV1(forced expiratory volume in 1 second), maximal inspiratory pressure (MIP) and maximal expiratory pressure (MEP).
- *Mean change from baseline on muscle strength by manual muscle test (MMT) and Hand-Held dynamometry.*

Functional Assessment :

Functional assessments will be obtained according to the Protocol Schedule of Activities. In order to provide optimal testing conditions and consistency in endpoint measurements, the functional assessments will be performed after the MRI and before needle muscle biopsy whenever possible. All functional assessments will be conducted by a trained physiotherapist.

Pulmonary Function

Pulmonary function testing will be completed to evaluate the maximal lung function recording FVC, FEV1, MIP and MEP.

4 Stair Climb (4 SC)

The 4 SC quantifies in seconds the time required for a subject to ascend 4 standard steps. The method the subject uses (eg, using the hand rails) to climb the stairs is recorded to understand any change in technique that occurs over time.

Two Minute Walk Test (2MWT)

The 2-minute walk test (2MWT) is a shorter measure of walking performance than the 6-minute walk test (6MWT). In this test, subjects start from a clearly marked line of tape on the

floor and walk up and down a 21 meter hallway for 2 minutes at a fast but comfortable speed wearing their regular footwear.

10-meter walk/run

The 10-meter walk/run is a frequently used timed function test in muscular dystrophy trials demonstrating good test-retest reliability in several different populations and has been used in studies of LGMD21^{19,27}. Individuals are instructed to walk at a fast but comfortable speed in a long cooridor with an even surface. Measurement of time begins at a still-standing start and stops when the individual passes the 10-meter mark while continuing to walk 2.5 meters beyond the mark.

Timed Up & Go (TUG)

The Timed Up & Go is a measure of hip strength as well as dynamic balance. This timed function test has good test-retest reliability and has been used in studies of LGMD21^{19,27}. The individual is asked to rise from a seated position in a standardized armchair (44-45 cm), walk at a comfortable and safe pace to a tape mark on the floor 3 meters away, turn around the mark, go back to the chair, turn and sit down.

Strength Assessment

Muscle strength will be quantified by means of manual muscle testing (MMT) quantified by the modified Medical Research Council (MRC) scale and by handheld dynamometer quantified in pounds (lbs). The following muscle groups will be evaluated: shoulder abduction, elbow flexion, elbow extension, hip extension, hip flexion, knee extension, knee flexion.

Performance of Upper Limb (PUL)

The PUL scale has been devised to assess motor performance of the upper limb. Motor performance will be impacted by muscle strength and contractures and the scale aims to incorporate performance of shoulder, elbow, wrist and hand function.

For all the above endpoints except forced vital capacity, more than one assessment may be performed at the site. If more than one assessment is performed, the site is to record the best (maximum) score in the case report forms. For the forced vital capacity, 3 attempts will be made and the percent predicted will be calculated based on the maximum forced vital capacity.

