- m. Prep B1.5 (K2 EDTA plasma collection optimized for biomarker/proteomic/metabonomic analysis) will be collected at: Cohort 1 at Visits 2 (baseline), 7 (Day 113), 10 (Day 197), 15 (Day 337) and 18 (Day 421) and Cohort 2 and 3 at Visit 2 (baseline), 7 (Day 113) and 10 (Day 197)
  Prep B2.5 (serum collection optimized for biomarker/ proteomics/metabonomic analysis) will be collected at: Cohort 1 at Visits 2 (baseline), 7 (Day 113), 10 (Day 197), 15 (Day 337) and 18 (Day 421) and Cohort 2 and 3 at Visit 2 (baseline), 7 (Day 113) and 10 (Day 197)
  Prep R1 (PAXGene whole blood collection optimized for RNA analysis) will be collected at: Cohort 1 at Visits 2 (baseline), 10 (Day 197)
  Prep 4 (Cell-free RNA) will be collected at: Cohort 1 at Visits 2 (baseline) ) and 10 (Day 197)
  Prep 4 (Cell-free RNA) will be collected at: Cohort 1 at Visits 2 (baseline) ) and 10 (Day 197)
  Prep 4 (Cell-free RNA) will be collected at: Cohort 1 at Visits 2 (baseline) ) and 10 (Day 197)
  Prep 4 (Cell-free RNA) will be collected at: Cohort 1 at Visits 2 (baseline) ) and 10 (Day 197)
  Prep 4 (Cell-free RNA) will be collected at: Cohort 1 at Visits 2 (baseline) ) and 10 (Day 197)
  Prep 4 (Cell-free RNA) will be collected at: Cohort 1 at Visits 2 (baseline) ) and 10 (Day 197)
  - Prep D1.5 (K2 edetic acid (ethylenediaminetetraacetic acid) (EDTA) whole blood collection optimized for DNA analysis) will be collected at the Screening visit.
- n Timed Function tests and PUL will be repeated on Day 2 of Visit 3 prior to the first dose.
- o MRI of the liver is performed on Visit 11 only (and not on Visit 3) for Cohort 1.

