#### **Prior to dosing, the following procedures will be completed:**

- Physical Examination, including Nose and Throat Mucosal Exam
- **Pregnancy Test**: A highly sensitive urine pregnancy test will be performed on all female subjects
- Diary Cards: For collection of first day of each menstrual cycle for WOCBP.
- Contraception Review: Confirmation of use of acceptable forms of contraception
- Weight
- Vital signs: Supine blood pressure, pulse rate, respiratory rate, and oral temperature.
- **12-lead ECG:** ECGs will be performed in triplicate
- Clinical laboratory tests:
  - Hematology with complete blood count and differential, comprehensive metabolic panel (sodium, potassium, chloride, carbon dioxide, blood urea nitrogen, creatinine, calcium, glucose, total protein, albumin, total bilirubin, AST, ALT, alkaline phosphatase) gamma-glutamyl transferase (GGT), prothrombin time (PT), activated partial thromboplastin time (aPTT), creatine kinase, amylase, cardiac troponin I. Urinalysis.
- Serum ferritin, serum iron, % transferrin saturation, TIBC: fasting blood collection
- Horomone Testing: LH, FSH, estrogen in WOCBP
- GLDH
- **Fecal occult blood**: Fecal sample is to be collected at home within 1 week prior to scheduled visit.
- C-SSRS

- Immunogenicity: Baseline
- PD sample collection: Predose
- PK sample collection: Predose
- **MRI-liver**: Liver MRI will be obtained for iron accumulation (visit 11 only)
- **MRI-muscle:** WB-MRI and dedicated thigh MRI will be performed for muscle quantity and quality
- **DXA Whole Body:** Whole body DXA will be performed for lean body mass.
- **DXA Spine and Hip:** Spine and hip DXA will be performed for BMD.
- **Functional assessments:** Must be conducted in the following order: Respiratory function (FVC, FEV1, MIP, MEP), 4SC, 2MWT, 10-meter walk/run, TUG, strength assessment (MMT, hand-held dynamometry) and PUL.
- Quality of Life assessments
  - InQol
  - SF-36

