Tuble	Table 14.1.1.68	Limb(PUL)	1110
Table		Mean Performance of Upper Limb(PUL)	FAS
		Mixed Model Repeated Measures (MMRM) of Change from	
	Table 14.1.1.69	Baseline	
Table		Mean Performance of Upper Limb(PUL)	Completer Population
		Mixed Model Repeated Measures (MMRM) of Change from	1 1
	Table 14.1.1.70	Baseline	
Table	Table 14.1.1.71	Listing of Performance of Upper Limb	FAS
Listing		Listing of items, Description and Scores Performance of	
	Table 14.1.1.72	Upper Limb	
Figure		Plot of Mean Absolute Value on Performance of Upper	FAS
	Figure 14.1.1.8	Limb(PUL)	
Figure		Plot of Mean Change from Baseline on Performance of Upper	FAS
	Figure 14.1.1.9	Limb(PUL)	
Table	Table 14.1.1.73	Summary of absolute value for Timed Up & Go (TUG)	FAS
Table	Table 14.1.1.74	Mean Change from Baseline for Timed Up & Go (TUG)	FAS
Table		Mean Timed Up & Go (TUG)	FAS
		Mixed Model Repeated Measures (MMRM) of Change from	
	Table 14.1.1.75	Baseline	
Table		Mean Timed Up & Go (TUG)	Completer Population
		Mixed Model Repeated Measures (MMRM) of Change from	
	Table 14.1.1.76	Baseline	

Figure	Figure 14.1.1.10	Plot of Mean Absolute Value on Timed Up & Go (TUG)	FAS
Figure	1 iguie 14.1.1.10	Plot of Mean Change from Baseline on Timed Up & Go	FAS
riguit	Figure 14.1.1.11	(TUG)	1110
Table	Table 14.1.1.77	Summary of absolute value for for10-meter walk/run (10MR)	FAS
Table	Table 14.1.1.78	Mean Change from Baseline for10-meter walk/run (10MR)	FAS
Table	14010 1 1111110	Mean 10-meter walk/run (10MR)	FAS
1		Mixed Model Repeated Measures (MMRM) of Change from	
	Table 14.1.1.79	Baseline	
Table		Mean 10-meter walk/run (10MR)	Completer Population
		Mixed Model Repeated Measures (MMRM) of Change from	1 1
	Table 14.1.1.80	Baseline	
Figure	Figure 14.1.1.12	Plot of Mean Absolute Value on 10-meter walk/run (10MR)	FAS
Figure	~	Plot of Mean Change from Baseline on 10-meter walk/run	FAS
0	Figure 14.1.1.13	(10MR)	
Table		Summary of absolute value for Two Minute Walk Test	FAS
	Table 14.1.1.81	(2MWT)	
Table		Mean Change from Baseline for Two Minute Walk Test	FAS
	Table 14.1.1.82	(2MWT)	
Table		Mean Two Minute Walk Test (2MWT)	FAS
		Mixed Model Repeated Measures (MMRM) of Change from	
	Table 14.1.1.83	Baseline	
Table		Mean Two Minute Walk Test (2MWT)	Completer Population
		Mixed Model Repeated Measures (MMRM) of Change from	
	Table 14.1.1.84	Baseline	
Figure		Plot of Mean Absolute Value on Two Minute Walk Test	FAS
	Figure 14.1.1.14	(2MWT))	
Figure		Plot of Mean Change from Baseline on Two Minute Walk	FAS

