	Figure 14.1.1.15	Test (2MWT)	
Table	Table 14.1.1.85	Summary of absolute value for 4 Stair Climb (4SC)	FAS
Table	Table 14.1.1.86	Mean Change from Baseline for 4 Stair Climb (4SC)	FAS
Table		Mean 4 Stair Climb (4SC)	FAS
	T-11. 14 1 1 07	Mixed Model Repeated Measures (MMRM) of Change from	
Table	Table 14.1.1.87	Baseline	Commission Doministra
Table		Mean 4 Stair Climb (4SC) Mixed Model Repeated Measures (MMRM) of Change from	Completer Population
	$T_{abla} 141199$	Baseline	
Figure	Table 14.1.1.88 Figure 14.1.1.16	Plot of Mean Absolute Value on 4 Stair Climb (4SC)	FAS
Figure	Figure 14.1.1.16 Figure 14.1.1.17	Plot of Mean Change from Baseline on 4 Stair Climb (4SC)	FAS
Table	11guit 14.1.1.1/	Summary of absolute value for Forced Expiratory Volume in	FAS
1 able	Table 14.1.1.89	1 second (FEV1)	IAU
Table	1 4010 17.1.1.07	Mean Change from Baseline for Forced Expiratory Volume in	FAS
1 4010	Table 14.1.1.90	1 second (FEV1)	1710
Table	14010 1 11111.00	Mean Forced Expiratory Volume in 1 second (FEV1)	FAS
		Mixed Model Repeated Measures (MMRM) of Change from	
	Table 14.1.1.91	Baseline	
Table		Mean Forced Expiratory Volume in 1 second (FEV1)	Completer Population
		Mixed Model Repeated Measures (MMRM) of Change from	r ···· · · r
	Table 14.1.1.92	Baseline	
Figure		Plot of Mean Absolute Value on Forced Expiratory Volume	FAS
0	Figure 14.1.1.18	in 1 second (FEV1)	
Figure	 	Plot of Mean Change from Baseline on Forced Expiratory	FAS
0	E	Volume in 1 second (FEV1)	
	Figure 14.1.1.19		
Table	Figure 14.1.1.19		FAS
Table	Table 14.1.1.93	Summary of absolute value for Maximal Inspiratory Pressure (MIP)	FAS

		Pressure (MIP)	
Table		Mean Maximal Inspiratory Pressure (MIP)	FAS
Table		Mixed Model Repeated Measures (MMRM) of Change from	1710
	Table 14.1.1.95	Baseline	
Table		Mean Maximal Inspiratory Pressure (MIP)	FAS
		Mixed Model Repeated Measures (MMRM) of Change from	
	Table 14.1.1.96	Baseline	
Figure		Plot of Mean Absolute Value on Maximal Inspiratory	FAS
	Figure 14.1.1.20	Pressure (MIP)	
Figure		Plot of Mean Change from Baseline on Maximal Inspiratory	FAS
m 11	Figure 14.1.1.21	Pressure (MIP)	
Table	T-1-1-14-1-1-07	Summary of absolute value for Maximal Expiratory Pressure	FAS
Table	Table 14.1.1.97	(MEP) Mean Change from Baseline for Maximal Expiratory Pressure	FAS
Table	Table 14.1.1.98	(MEP)	ГАЗ
Table	14010 14.1.1.98	Mean Maximal Expiratory Pressure (MEP)	FAS
Table		Mixed Model Repeated Measures (MMRM) of Change from	1745
	Table 14.1.1.99	Baseline	

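### SAP 6.2 equates the best score with the maximum, which for the three timed tests (4SC, 10MR, TUG) is the slowest trial

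*SAP*

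**What the plan says.** After describing the functional, pulmonary and strength tests, SAP 6.2 sets one recording rule: "If more than one assessment is performed, the site is to record the best (maximum) score in the case report forms". It covers every endpoint in that section except FVC, which has its own rule (three attempts, largest value used). Repeat assessments are allowed, not required.

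Three of the covered tests are timed:

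- 4SC: "The 4 SC quantifies in seconds the time required for a subject to ascend 4 standard steps".
- 10MR: "Measurement of time begins at a still-standing start and stops when the individual passes the 10-meter mark".
- TUG: "This timed function test has good test-retest reliability". No unit is stated, but the test is called timed.

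Neither document converts these times to speeds. Protocol 7.7.2 to 7.7.4 describes the same tests and has no rule for choosing among trials.

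SAP Appendix 1 plans absolute-value summaries for TUG, 10MR and 4SC (Tables 14.1.1.73, 14.1.1.77 and 14.1.1.85) and plots of mean absolute values (Figures 14.1.1.10, 14.1.1.12 and 14.1.1.16). SAP 8.2.2 models change from Visit 3, with the lead-in change (Visit 3 minus Visit 2) as a covariate.

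Visit 3 has two testing days for some of these endpoints. Footnote n to the Protocol's Schedule of Activities says: "Timed Function tests and PUL will be repeated on Day 2 of Visit 3 prior to the first dose". The Version 3 entry in the Protocol's Document History gives test-retest reliability as the reason. SAP 8.2.2 refers to Visit 3 without naming a session.

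**The concern.** For a time, smaller is better. The words *best* and *maximum* in the SAP 6.2 rule therefore point to different trials for 4SC, 10MR and TUG, and nothing else in the documents settles which one goes into the CRF. Followed literally, the parenthesis sends the slowest trial to the database. The rule sends one score forward, so the CRF alone would not show which reading the site had used.

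Two things are at stake. The absolute-value tables and plots would show slower times than intended. Change scores would move if the reading or the number of trials were not the same at each visit, and an ambiguous rule with an optional number of trials secures neither.

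A smaller gap is that the SAP does not say which Visit 3 session is the reference for 4SC, 2MWT, 10MR, TUG and PUL.

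**Working it through.** **1. Direction of each endpoint under the rule.** For FEV1, MIP, MEP, 2MWT, PUL, manual muscle testing and dynamometry, a larger value is better, so best and maximum agree. For 4SC, 10MR and TUG a smaller value is better, so they conflict. The conflict is confined to three endpoints.

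**2. Inputs for a size.** The plan has no figure to reproduce: Protocol 9.1 gives no sample size calculation, and neither document gives an SD, a number of trials or a correlation for these tests. Assumptions: normal trial errors with within-subject SD *s*, correlation *r* between trials in a session, *k* trials, and no practice or fatigue effect.

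**3. Effect on the recorded level.** The expected maximum of *k* standard normal values is 1/√π = 0.564 for *k* = 2 and 3/(2√π) = 0.846 for *k* = 3. The expected gap between slowest and fastest trial is 2 × E[max] × √(1 − *r*) × *s*:

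| Trials | r = 0 | r = 0.5 | r = 0.8 |
|---|---|---|---|
| 2 | 1.13 s | 0.80 s | 0.50 s |
| 3 | 1.69 s | 1.20 s | 0.76 s |

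For example, with two trials and *r* = 0, an assumed *s* of 0.3, 0.5 or 1.0 seconds gives a gap of 0.34, 0.56 or 1.13 seconds. This gap passes straight into the absolute-value tables and plots.

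**4. Effect on change from Visit 3.** Write the recorded value at a visit as the true value plus a selection shift *b*, where *b* is +E[max]√(1 − *r*)*s* for the slowest trial and minus that for the fastest. With no true change, Visit 7 minus Visit 3 is shifted by *b* at Visit 7 minus *b* at Visit 3.

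- Same reading and same *k* at both visits: shift 0.
- Fastest trial at both visits, but one trial at Visit 3 and two at Visit 7: −0.564√(1 − *r*)*s*, or −0.56, −0.40 and −0.25 *s* for *r* = 0, 0.5 and 0.8.
- Slowest at Visit 3 and fastest at Visit 7, two trials each: the full gap in the table, −1.13, −0.80 and −0.50 *s*.

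The last two cases are hypothetical. Nothing in either document plans a switch of reading or unequal trial counts. They show what the wording leaves open.

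**5. Which Visit 3 session.** The baseline rules in SAP 6.1.1, 6.1.2, 6.2.3 and 8.2.1 cover vital signs, ECG, echocardiogram, laboratory, pharmacodynamic and safety data, not functional tests. The baseline text in SAP 8 defines 16-week intervals and names no session. Protocol 6.3 has the first Visit 3 session run the full battery: "Must be conducted in the following order: Respiratory function (FVC, FEV1, MIP, MEP), 4SC, 2MWT, 10-meter walk/run, TUG, strength assessment" and then PUL. Visits 2, 7 and 11 use the same order (Protocol 6.2, 6.7, and 6.3 or 6.8). The Day 2 session omits respiratory and strength testing, so the first session is the like-for-like reference.

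**The case against.** The strongest reply is that *best* is the operative word and *maximum* only a gloss. The tests are done by trained physiotherapists, who would be expected to take the fastest time as the best. Repeat trials are optional and Protocol 7.7.2 to 7.7.4 schedules none, so the rule may seldom apply. The absolute-value displays are descriptive, and the modelled quantity is change, where a consistent choice cancels. All of this stands. It limits the consequence but leaves the contradiction in the rule.

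A reader might infer three stronger things that the documents do not support.

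- *That slow trials will be recorded and the efficacy results biased.* The wording permits that reading but does not show that any site would use it. Change scores move only under the hypothetical conditions in step 4.
- *That the maximum is to be taken across the two Visit 3 days.* With one trial per day and uncorrelated errors, that would shift Visit 3 by 0.56 *s*. Visit 3 enters the lead-in change and the first treatment change with opposite signs, so the contrast between them would shift by 2 × 0.564 = 1.13 *s*. The SAP does not plan such pooling. The Protocol describes the Day 2 tests as a repeat and gives test-retest reliability as their purpose, which points to the first session as the study measurement.
- *That a wrong entry could never be put right.* Protocol 11.1 requires CRF data to match the source documents, so recovery may be possible from source, though not from the CRF alone.

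On the Visit 3 session, the SAP's last-pre-dose convention for other data would by analogy select Day 2. That is a reason to name the session; it does not show that the plan is wrong.

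**Conclusion.** The recording rule is wrong as written for 4SC, 10MR and TUG: it contradicts itself and, taken literally, selects the slowest trial. The conclusion rests on the SAP's own descriptions of the tests; only 4SC has an explicit unit, while 10MR and TUG are plainly timed.

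The direct effect is on the descriptive absolute-value tables and plots for these three secondary endpoints. Its illustrative size is 0.50 to 1.13 within-subject SD with two trials and 0.76 to 1.69 with three, under normal errors and within-session correlations from 0.8 down to 0. Change scores are unaffected when the reading and the number of trials are the same at each visit. Primary safety endpoints and FVC are not touched.

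This is a wording correction worth making, not a threat to the trial's main conclusions. The Visit 3 session is a minor clarification.

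**What to change.** In SAP 6.2 and the CRF completion instruction, replace the rule with:

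> Best means the shortest time for 4SC, 10MR and TUG, and the largest value for 2MWT, FEV1, MIP, MEP, strength and PUL. It is selected within a single session, with the same number of trials at every visit.

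The equal trial count is needed because cancellation in change scores depends on it.

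In SAP 8.2.2, as a minor clarification:

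> For 4SC, 2MWT, 10MR, TUG and PUL, the Visit 3 value comes from the first Visit 3 session. The Day 2 repeat is used for test-retest reliability only, and no best value is taken across the two days.

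The essential request is that one session be named. The first is preferred because its battery matches Visits 2, 7 and 11, and because it exists for any subject whose Visit 3 came before Version 3 added the second day.

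The cost is a few lines of SAP text and a CRF note. The tests are performed as before, although the number of trials has to be fixed if it now varies. If slowest-trial values may already have been entered, those entries need checking against source records.
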